7. STUDY DESIGN

We will perform a mixed-methods cohort study to explore the feasibility of EMCAT for measuring between-group differences in postoperative recovery, its potential to guide follow-up type (face-to-face, telemedicine or patient-initiated) in open carpal tunnel decompression, and its potential to guide follow-up timing after steroid injection for TBOA. The study setting will be NHS hospitals in the England, Scotland and Wales.

Our primary objective is to use EMCAT to compare the recovery trajectories of patients undergoing PNF and LF for Dupuytren's disease. We expect to see a difference in recovery trajectory over a 12-week period, with patients undergoing PNF showing less severe symptoms than those undergoing LF over the first 4 weeks. To meet this objective, we will recruit 396 participants (198 undergoing PNF and 198 undergoing LF), who will be followed up for a 12-week period with daily EMCAT assessments.

To address our secondary objectives, we will simultaneously recruit patients undergoing:

- Steroid injection for TBOA
- Steroid injection for trigger finger
- Trapeziectomy for TBOA
- Arthroplasty for TBOA
- Surgical release of trigger finger
- Open CTD
- Minimally invasive (endoscopic or percutaneous) CTD

We will recruit as many participants as we can in these groups, within the limits of the study timing and funding, and up to a maximum of 198 per group. We will use all collected EMCAT data to test the following hypotheses:

- Steroid injection results in less severe post-treatment symptoms than trapeziectomy, within the first 4 weeks
- Trapeziometacarpal arthroplasty results in less severe post-treatment symptoms than trapeziectomy, within the first 4 weeks
- Minimally invasive (endoscopic or percutaneous) CTD results in less severe post-treatment symptoms than open CTD, within the first 2 weeks
- The difference in the recovery of groups undergoing open release vs steroid injection for trigger finger are not clinically significant over the first 2 weeks

The objective is to test EMCAT's ability to differentiate between recovery trajectories that are expected to differ, rather than to prove or disprove that differences in recovery trajectory exist. The clinical comparisons are a vehicle for testing the measurement properties of EMCAT.

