11.4 Description of the Statistical Methods

The hypotheses outlined in the primary and secondary objectives will be tested with mixed-effects linear modelling. These models will comprise: EMCAT score (continuous dependent variable on a logit scale, derived from a graded response model); participant number (random intercept); age, sex, and baseline score (fixed effects); and an interaction term between time (number of days following the intervention) and treatment allocation. Marginal means will be derived from these models and between-group differences calculated at daily timepoints after Tukey adjustment for multiplicity. This will be performed with the *emmeans* R package, or equivalent software. For each comparison, marginal means will be plotted, and differences compared to a minimal important difference (MID) estimate of half a standard deviation of baseline scores. Clinically and statistically significant (at the 5% level) differences will be compared to those predicted (see section 6).

EMCAT completion rates (number of completed response sets divided by number of invitations), response times, and UES scores will be analysed through descriptive statistics. The UES was originally intended to measure 6 user engagement constructs, but subsequent studies have suggested that it follows a 4-factor structure. Items of the UES will be grouped into the 4 subscales described by O'Brein et al, to measure: focused attention, aesthetic appeal, perceived usability and reward⁵.

The criterion validity of the EMCAT scores against the full-length PEM scores will be assessed by comparing pairs of EMCAT scores and full-length PEM scores that were obtained from the same participant on the same day. Comparison will be made by calculating Pearson's correlation coefficient, mean absolute error, root mean squared error and the Bland-Altman method⁶.

In Stream 2, three independent clinicians will review EMCAT trajectories (presented as time series plots) and follow-up appointment dates for participants that underwent open CTD. They will be asked to predict whether a change in management was required at the follow-up appointment. We will calculate inter-rater reliability of these assessments (Fleiss' kappa) and, for each clinician, the accuracy, sensitivity, specificity, positive predictive value and negative predictive value of their predictions against the reference standard (whether or not the patient received a change in management).

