11.5 Sample Size Determination

Our primary objective is to use EMCAT to compare the recovery trajectories of patients undergoing PNF and LF for Dupuytren's disease. To have a 90% chance of detecting a moderate effect size of 0.35 between groups on a z-score scale (with a standard deviation of 1), at the 5% significance level, 344 patients are required for each comparison (172 per group). Assuming a 15% attrition, this leaves a target sample size of 396 for the primary objective (198 per group).

Objective 2 (see section 6) sets out 4 more comparisons, involving 7 other groups of patients:

- Steroid injection for TBOA
- Steroid injection for trigger finger
- Trapeziectomy for TBOA
- Arthroplasty for TBOA
- Surgical release of trigger finger
- Open carpal tunnel decompression
- Minimally invasive (endoscopic or percutaneous) carpal tunnel decompression

At 198 participants per group, and 9 groups total, a further 1386 participants (1782 total) would be required to reach statistical significance in all of our secondary (non-essential) objectives. We will recruit as many participants as we can in these groups, within the limits of the study timing and funding, and up to a maximum of 198 per group.

In summary, our recruitment target is 396 (172 participants undergoing LF and 172 participants undergoing PNF), but we will recruit up to a maximum of 1782 participants (198 in each of the groups described above).

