11.9 The Level of Statistical Significance

Clinical Research Protocol Template version 15.0

CONFIDENTIAL

© Copyright: The University of Oxford and Oxford University Hospitals NHS Foundation Trust 2019 Page 24 of 33 Statistical significance will be defined at the 5% level.

11.10 Procedure for Accounting for Missing, Unused, and Spurious Data.

Data which are clearly spurious will be excluded. Missing data will be described. For each variable, the association of missingness and the values of other variables will be analysed through descriptive statistics. All available data will be used to fit the models used for the primary analysis. We will not impute missing data and do not plan to undertaken any sensitivity analyses.

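### With two groups compared on each day the Tukey adjustment changes nothing, and no single primary contrast is named to match a sample size built on one 5% test

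*Protocol*

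**What the plan says.** Section 11.4 specifies a mixed-effects linear model for the EMCAT score. It has a participant random intercept, fixed effects for age, sex and baseline score, and "an interaction term between time (number of days following the intervention) and treatment allocation". Marginal means are taken from the model, with "between-group differences calculated at daily timepoints after Tukey adjustment for multiplicity". On software it adds: "This will be performed with the *emmeans* R package, or equivalent software". Differences are set against a minimal important difference (MID) of half a baseline standard deviation. Those that are clinically and statistically significant are then compared with the predictions in section 6.

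Section 7 gives the primary comparison two groups: "we will recruit 396 participants (198 undergoing PNF and 198 undergoing LF"), "who will be followed up for a 12-week period with daily EMCAT assessments". The expected result is "patients undergoing PNF showing less severe symptoms than those undergoing LF over the first 4 weeks".

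Section 11.5 states that, for 90% power at an effect of 0.35 SD, "at the 5% significance level, 344 patients are required for each comparison (172 per group"). Section 11.9 says only: "Statistical significance will be defined at the 5% level". Section 11.3 states that no separate SAP is in use, so section 11.4 is the whole analysis plan on this point.

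**The concern.** Tukey's method protects against comparing many group means within one family. When two groups are compared on a given day, the family holds one pair and there is nothing to adjust. The multiplicity in this design runs across days, and the stated adjustment does not reach it. The protocol therefore claims an error control that it does not have.

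The primary hypothesis also lacks a defined test. The plan names no primary day, no summary over the four-week window, and no rule for how many days must differ. The sample size, by contrast, rests on exactly one test. At stake is whether the 5% error rate and 90% power quoted for the primary objective describe the analysis that will be reported.

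**Working it through.** **Inputs from the protocol.** Two groups (section 7); daily assessment for 12 weeks, so 12 × 7 = 84 days; primary window of 4 weeks, so 28 days; effect 0.35, SD 1, power 90%, level 5%, 172 per group (section 11.5); MID 0.5 baseline SD (section 11.4).

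**Assumptions, not in the protocol.** Within-person correlation of daily scores 0.3 to 0.95. Time either a factor or a straight line, because section 11.4 does not say which. Baseline SD equal to the SD of 1 used for the sample size.

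**1. Reproduce the sample size.** n per group = 2 × (1.960 + 1.282)² / 0.35² = 171.5, rounded up to 172. This is the protocol's figure. A one-sided test would give 140. The stated number is therefore one two-sided 5% test, and power at 172 per group is 90%.

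**2. Tukey with two means.** The critical |t| is the 95% point of the studentized range for k means, divided by √2.
- k = 2: 1.960 in large samples, 1.967 at 342 degrees of freedom. Both equal the unadjusted values.
- At t = 2.5 and 342 degrees of freedom, the Tukey and plain p-values are both 0.0129.
- For contrast, k = 3 gives 2.354.

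**3. Chance of at least one false significant day, every day at two-sided 5%, no true difference.**

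Day as a factor, with equal correlation between days (simulated):

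| Assumed correlation | Days 1-28, either direction | Days 1-28, predicted direction only | Days 1-84, either direction |
|---|---|---|---|
| 0.3 | 64% | 34% | 92% |
| 0.5 | 49% | 25% | 74% |
| 0.7 | 33% | 16% | 48% |
| 0.9 | 17% | 8% | 22% |
| 0.95 | 12% | 6% | 15% |

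Time as one linear term, model correct, correlation 0.3 to 0.9: about 5-6% over days 1-28 and 5.5-8% over days 1-84. The inflation is small because every daily difference comes from the same two parameters.

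**4. If a day must be significant and also reach the MID.** The standard error of a one-day difference is √(2/172) = 0.108.
- Under no difference, 0.5 SD is 0.5 / 0.108 = 4.6 standard errors. In the simulation, a day this large in the predicted direction within days 1-28 occurred in about 0.01% of runs or fewer.
- Under a true 0.35 SD difference, the chance that a given day's estimate reaches 0.5 is 1 − Φ((0.5 − 0.35) / 0.108) = 1 − Φ(1.39) = 8%.

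This rule almost removes false positives, but the 90% power of section 11.5 does not describe it.

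**The case against.** The strongest reply is that the practical error may be small. Section 11.4 describes time as a number of days, which reads most naturally as numeric, and a correct straight-line model gives about 5-6% over the primary window. The hypothesis is directional, so a day favouring LF would not confirm it, which roughly halves the factor-model rates. Section 11.4 also pairs statistical with clinical significance. Section 6 adds that the clinical comparisons are a vehicle for testing the instrument, in a non-randomised study. All of this stands. It limits the size of the problem and lowers its severity, but it neither makes the Tukey step work nor supplies a primary test.

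Three stronger readings are tempting and are not supported:

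- A reader might infer that any single significant day could be reported as success. The text does not say so, and its pairing with the MID suggests otherwise. It does not settle the matter, because it never states whether both criteria must hold on the same day or how many days count.
- A reader might take Tukey to run over all 2 × 84 = 168 group-by-day means. That family has 168 × 167 / 2 = 14,028 pairs and a critical value of about 4.52. Single-day power would then be Φ(0.35 / 0.108 − 4.52) = about 10%. The protocol does not describe this family, so the 10% figure should not be attributed to the plan.
- A reader might conclude that Tukey is idle throughout. It would act if the three thumb-base groups shared one model. The point here concerns two-group comparisons, including the primary one.

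**Conclusion.** The point holds in limited form. For the primary comparison the stated Tukey adjustment equals no adjustment, nothing controls error across 28 or 84 days, and no contrast is named that matches the single two-sided 5% test behind 172 per group. These statements follow from the protocol alone, on the natural reading that groups are compared within each day.

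The size of the inflation is not fixed by the protocol. Over days 1-28 it runs from near zero (MID also required), through about 5-6% (correct linear time), to 12-64% (day as a factor, assumed correlation 0.95 to 0.3). No single percentage should be quoted without those conditions. Where the inflation vanishes because the MID is also required, the stated power ceases to apply. The plan should be corrected, but the defect is one of specification and does not invalidate the design.

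**What to change.** In section 11.4:

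1. Delete the Tukey wording.
2. Name one primary test: the model-based PNF-LF difference averaged over days 1-28, at two-sided 5%.
3. For the secondary superiority hypotheses, use the average over days 1-28 (the two thumb-base comparisons) or days 1-14 (carpal tunnel), matching their stated windows.
4. For trigger finger, where the prediction is no clinically significant difference, compare the confidence interval of the day 1-14 average with plus and minus the MID. A non-significant superiority test cannot support that prediction.
5. Present daily differences as a descriptive plot with simultaneous bands across days.

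A single averaged contrast needs no adjustment across days and fits the one-test basis of section 11.5. That section does not itself specify an averaged outcome. A 28-day mean has a smaller SD than one day's score: √(ρ + (1 − ρ)/28) is 0.72 at an assumed correlation ρ of 0.5 and 0.95 at 0.9. Under the same equal-correlation assumption, 172 per group would then give about 99% and 93% power for a difference of 0.35, so the existing target remains adequate.

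The cost is a few sentences in section 11.4, with no extra participants or data. What is given up is the ability to claim significance for individual days.

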9.6.1 Description of study procedure(s)

EMCAT is a progressive web application maintained by the University of Cambridge Psychometrics Centre. Each day for the first 12 weeks, it will prompt participants to complete an assessment, either by email and/or push notification. Participants undergoing steroid injection for TBOA will receive twiceweekly notifications for a further 12 weeks. When a participant receives a notification, they can choose to engage with the EMCAT app, or dismiss the notification. Those who choose to engage will either click on a hyperlink in an email, or on a push notification button to start the assessment. The application will pose questions from the PEM questionnaire which the participant will be able to respond to by clicking response options (See Appendix A).

After each response, the application will automatically select the next most useful question to administer. This process is continued until a prespecified stopping rule is met (standard error of measurement < 0.3). We expect that participants will be asked to complete between 1 and 4 questions each time they are notified. EMCAT responses will be collected for a period of 12 weeks (24 weeks for those undergoing steroid injection for TBOA). We may vary the time of day these notifications are scheduled for throughout the study, to reduce server demands.

In addition to the PEM EMCAT, each participant will be asked to complete the full-length PEM part 2 questionnaire (11 questions) at 0, 6 and 12 weeks via the app. At 12 weeks, we will ask participants to complete the User Engagement Scale (UES, 31 questions), also via the app. It is possible that participants who have had a negative experience of the app do not return UES data through it. Therefore, participants who do not respond to the UES via the app will be contacted via email and/or telephone and offered the opportunity to complete the UES either through the app reminder, over email or over the telephone. The method of response to the UES will be recorded, if not through the EMCAT platform.

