9.12 Study sequence

- 1. Potential participants will be identified by clinical members of the research team during routine care.
- 2. The clinical team members will invite potential participants to participate on the day of their treatment.
- 3. Potential participants will be provided with a written information pack, and given time to read this and discuss it.
- 4. The investigator will take informed consent from the participant at that point, if the participant feels they have had sufficient time to consider taking part.

- 5. At the point of recruitment, a member of the research team will assist the participant in downloading the EMCAT app and enabling push notifications.
- 6. At the point of recruitment, prior to the treatment, the participant will complete the full-length (11-item) PEM part 2 via the EMCAT app, and a single EMCAT assessment.
- 7. Over the next 12 weeks, participants will complete daily PEM EMCAT questionnaires (if they choose to) when prompted by email or push notification.
- 8. In addition, at 6 and 12 weeks, participants will be asked to complete the full-length PEM part 2 via the app, separately.
- 9. At 12 weeks, participants will also be asked to complete the UES via the app. Participants who do not respond with 7 days will be contacted via email or telephone and asked if they would like to return UES responses either via email or over the telephone. The method of UES response (app/email/telephone) will be recorded, if not via the ECMAT platform.
- 10. At 12 weeks, notifications will stop for all participants except those who underwent steroid injection for TBOA these participants will continue to receive EMCAT notifications twice weekly for a further 12 weeks.
- 11. For participants undergoing steroid injection for TBOA or open CTD, at the 24-week timepoint, a clinical member of the research team will review the participant's medical record and record follow-up appointment dates and (for those who underwent open CTD) whether the follow up resulted in a change of management.
- 12. Three independent clinicians will review de-identified EMCAT trajectories and appointment dates for patients who underwent open CTD, and predict whether each participant required a change in management.
- 13. We will identify and approach 10 patients and 10 clinicians with invitations to take part in semistructured interviews – interviews will take place no later than 14 days after finishing use of the EMCAT platform.

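### EMCAT prompts end at 12 weeks, when the last full-length PEM is requested, so most late 12-week PEMs have no scheduled same-day EMCAT score for the criterion-validity analysis

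*Protocol*

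**What the plan says.** Objective 4 (protocol section 6) assesses EMCAT against the full-length PEM at baseline, 6 weeks and 12 weeks. Section 11.4 sets the pairing rule: "comparing pairs of EMCAT scores and full-length PEM scores that were obtained from the same participant on the same day". It gives no tolerance of a day or more.

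The two instruments run on these schedules:

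- **EMCAT prompts (section 9.6.1):** "Each day for the first 12 weeks, it will prompt participants to complete an assessment, either by email and/or push notification". Collection is bounded in the same section: "EMCAT responses will be collected for a period of 12 weeks (24 weeks for those undergoing steroid injection for TBOA").
- **End of prompts (section 9.12, step 10):** "At 12 weeks, notifications will stop for all participants except those who underwent steroid injection for TBOA". For that excepted group, "these participants will continue to receive EMCAT notifications twice weekly for a further 12 weeks".
- **Full-length PEM (section 9.6.1):** "each participant will be asked to complete the full-length PEM part 2 questionnaire (11 questions) at 0, 6 and 12 weeks via the app". Section 9.12, step 8, repeats the two later requests: "at 6 and 12 weeks, participants will be asked to complete the full-length PEM part 2 via the app, separately".

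At baseline both forms are completed at the recruitment appointment (section 9.7). No return window or reminder is stated for the full-length PEM. A follow-up step exists for the User Engagement Scale (UES) only (section 9.12, step 9): "Participants who do not respond with 7 days will be contacted via email or telephone". Section 11.3 states that there is no separate SAP, so the pairing rule and the schedule are both fixed in the protocol.

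**The concern.** A same-day rule works when the short form is prompted on whatever day the long form is returned. That is true at two of the three timepoints. At baseline both forms are taken together. At 6 weeks the daily prompts are still running, so a late PEM meets that day's prompt.

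At 12 weeks the arrangement breaks down. The prompts end at the point where the PEM is requested, and a PEM returned after they stop has no scheduled partner, except on the prompted days of the TBOA injection group. Such a PEM is a valid response that section 11.4 cannot use. Some lateness is plausible, because the 11-item PEM and the 31-item UES are requested together at 12 weeks.

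At stake is the number of pairs at one named timepoint of a secondary objective. Pairs lost this way cannot be recovered, since section 11.10 rules out imputation and the EMCAT score was never requested.

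**Working it through.** **1. Inputs**

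- Nine groups, at most 198 each, 1782 in total (section 11.5).
- Daily response r = 0.93, the feasibility study's median (section 5), used here as an average.
- Share of 12-week PEMs returned after prompts stop, L. The protocol gives no figure, so L = 5% to 50% is an assumption.
- Late PEMs are accepted and spread evenly over the following week, groups are equal in size, and all three PEMs are returned (assumptions).

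**2. The plan's own figure.** The protocol states no number of validity pairs. Its only sample size is for the primary comparison: 2 × (1.960 + 1.282)² / 0.35² = 171.6, so 172 per group and 344 in total. This reproduces. The figure of 344 serves below only as a base for illustration.

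**3. Who is affected.** Eight groups have no prompt after 12 weeks: 8 × 198 = 1584 of 1782 at full recruitment, including all 396 primary-objective participants. The TBOA injection group has two prompts a week, so a late PEM falls on a prompted day with probability 2/7 = 29%.

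**4. Share of 12-week PEMs with a same-day EMCAT**

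- Eight groups: (1 − L) × r
- TBOA injection group: (1 − L) × r + L × (2/7) × r
- Overall: (8 × first + second) / 9

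| Late share L | Eight groups | TBOA injection | Overall |
|---|---|---|---|
| 0% | 93% | 93% | 93% |
| 5% | 88% | 90% | 88% |
| 10% | 84% | 86% | 84% |
| 20% | 74% | 80% | 75% |
| 30% | 65% | 73% | 66% |
| 50% | 47% | 60% | 48% |

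**5. Share of all pairs lost over three timepoints.** With no lateness, expected pairs per participant are 1 (baseline) + 0.93 + 0.93 = 2.86. The loss is L × [(8 + 5/7)/9] × 0.93 / 2.86 = L × 0.968 × 0.325 = 0.315 L. This is 1.6%, 3.1%, 6.3%, 9.4% and 15.7% for L = 5%, 10%, 20%, 30% and 50%.

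**6. Effect on precision.** The approximate standard error of a Bland-Altman limit of agreement is √(3/n) × s, where s is the SD of the differences. Take the 344 participants of the primary groups, who have no later prompts.

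- 12 weeks alone: 344 × 0.93 = 320 pairs give 0.097s. At L = 5%, 304 pairs give 0.099s. At L = 20%, 256 pairs give 0.108s. At L = 50%, 160 pairs give 0.137s.
- Pooled over timepoints, ignoring clustering within participant: 344 + 320 + 320 = 984 pairs give 0.055s. Losing 16, 64 or 160 pairs (L = 5%, 20%, 50%) leaves 968, 920 or 824, with 0.056s, 0.057s or 0.060s.

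**The case against.** The strongest reply is that little is lost. Section 11.4 does not commit to separate estimates by timepoint, the baseline and 6-week pairs are protected, and the pooled standard error hardly moves even at 50% lateness. Every group is asked for the full-length PEM, so participants outside the primary comparison also add pairs. Objective 4 has no sample-size or precision target to miss. All of this stands, and it limits the point to an inexpensive improvement.

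A second reply is that EMCAT might be opened without a prompt. The protocol does not say whether this is possible. Section 9.6.1 describes starting only from an emailed link or a push notification, and outside the TBOA injection group it limits collection to 12 weeks. It therefore offers little support for relying on unprompted scores.

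A reader might infer more than the documents support:

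- **That every late 12-week PEM is lost.** The TBOA injection group keeps twice-weekly prompts to week 24, so some of its late PEMs can be paired.
- **That prompts end on the very day the PEM falls due.** Both are set at 12 weeks, but no day number is given for either.
- **That the 7-day UES step shows late PEMs are expected.** It is a follow-up of non-responders to another questionnaire. Section 9.6.1 explains it by possible negative experience of the app. It is not a grace period for the PEM.
- **That the surviving pairs give a biased agreement estimate, or that agreement is weakest in recovered patients.** Nothing in the protocol supports either. Those who pair at 12 weeks would be the prompter responders, but no mechanism is given by which their same-day agreement would differ.

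**Conclusion.** The point holds as a scheduling gap. A strict same-day pairing rule is combined with a prompt schedule that ends when the last criterion measure is requested. Outside the TBOA injection group, a 12-week PEM returned after prompts stop has no scheduled EMCAT partner.

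The cost is a modest loss of precision, confined to the 12-week timepoint. For an assumed 5% to 50% late, the paired share there falls from 93% to between 88% and 48%, or about 2% to 16% of all pairs. The size rests wholly on the assumed lateness, on the 93% response rate carrying over from the feasibility study, and on late PEMs being accepted. If almost all 12-week PEMs are returned while prompts still run, almost nothing is lost. This is a cheap improvement to a secondary objective. It is not an error in the plan and has no bearing on the primary comparison.

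**What to change.** Amend sections 9.6.1 and 9.12 (steps 8 and 10) in one of two ways:

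1. Deliver an EMCAT assessment together with the 12-week full-length PEM whenever that PEM is completed, as is done at baseline.
2. Or continue the daily EMCAT prompt until the 12-week PEM is returned, for at most 7 further days.

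In either case, state that EMCAT assessments obtained this way after week 12 are used only for the validity pairs. Extend the collection period in section 9.6.1 to match.

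The cost is a small change to app scheduling and a sentence or two of text. The first option adds one short assessment and no separate prompts. The second adds up to seven short prompts for late responders. That matters a little because section 9.10 lists response fatigue as a reason for withdrawal, and for late responders in the TBOA injection group it would temporarily replace the twice-weekly schedule. The first option is therefore the lighter one.

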5. Explore whether information provided by the EMCAT platform could have accurately predicted which patients required a change in management during open CTD follow up	Accuracy of independent clinician interpretation of EMCAT trajectories against observed patient management	2 weeks and 12 weeks, or whenever follow- up is timed
6. Explore whether information provided by the EMCAT platform could help to time follow-up appointments for TBOA injections to coincide with patient need	Plots comparing follow-up appointment dates to EMCAT trajectories	Over 24 weeks
7. Explore the patient and clinician perceptions of EMCAT-guided follow-up and clinical monitoring	Semi-structured interviews	

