Participants undergoing open CTD or steroid injection for TBOA will be automatically entered into a second research stream. Those undergoing steroid injection for TBOA will be followed up with twice weekly EMCAT assessments for a further 12 weeks (24 weeks total). In this stream, participants' medical records will be reviewed by members of the research team at 24 weeks. For patients with TBOA, EMCAT trajectories will be plotted as time series graphs, and follow-up appointment dates will be overlaid onto these plots. They will be inspected to see whether appointments coincide with peaks in symptom severity.

For patients undergoing open CTD, we will record whether the participant underwent any change in management as a result of their follow-up appointment (including but not limited to antibiotic prescription, reoperation, clinical investigation, arrangement of further clinical follow-up and hand therapy referral). We will then ask three independent clinicians to inspect de-identified EMCAT trajectories and predict whether or not the patient required a change in management at their follow up. We will calculate the accuracy of these predictions against what happened to the participant at their follow up.

A subsample of 10 participants recruited from the first and second research streams, and 10 clinicians, will be interviewed about their experiences of the platform. Interviews will follow a schedule that covers the following topics:

- Perceived value of the EMCAT as a data-capture platform
- Acceptability of EMCAT
- Perceived burden of EMCAT
- Facilitators and barriers to using EMCAT
- Areas for improvement within the EMCAT platform

- The potential for EMCAT's to guide follow-up in different scenarios (e.g. open CTD or steroid injections for TBOA)

Participants will be given opportunity to discuss any other aspects of the EMCAT platform they consider important.

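### Objective 5 (open CTD): plots and appointment dates shown to raters have no cut-off at the visit being judged, so post-visit information can enter the accuracy estimates

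*Protocol*

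**What the plan says.** Objective 5 (Protocol section 6) is exploratory. It asks whether EMCAT information could have identified the patients who needed a change in management during open CTD follow-up. Its timepoints are "2 weeks and 12 weeks, or whenever follow- up is timed".

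Three places describe what the raters receive:
- Section 7 has them "inspect de-identified EMCAT trajectories and predict whether or not the patient required a change in management at their follow up". It does not mention dates.
- Section 9.12, step 12: "Three independent clinicians will review de-identified EMCAT trajectories and appointment dates for patients who underwent open CTD".
- Section 11.4: "three independent clinicians will review EMCAT trajectories (presented as time series plots) and follow-up appointment dates for participants that underwent open CTD". It continues: "They will be asked to predict whether a change in management was required at the follow-up appointment".

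Section 11.4 then compares "their predictions against the reference standard (whether or not the patient received a change in management"). Section 7 lists what counts as a change resulting from the follow-up appointment: "including but not limited to antibiotic prescription, reoperation, clinical investigation, arrangement of further clinical follow-up and hand therapy referral".

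The appointment dates come from a medical record review at 24 weeks (section 9.12, step 11). Daily EMCAT for open CTD lasts 12 weeks; step 10 states that "At 12 weeks, notifications will stop for all participants except those who underwent steroid injection for TBOA". Section 11.3 says that no separate SAP is in use, so section 11.4 is the analysis plan for this objective.

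**The concern.** The objective concerns what a clinician could have known before the visit. A fair test gives raters only what existed at that moment. The protocol names the rater material without such a limit, and one item of that material, the appointment dates, overlaps with one item of the outcome definition.

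At stake are the accuracy, sensitivity, specificity and predictive values in section 11.4, and possibly Fleiss' kappa. They are the protocol's only quantitative assessment of whether EMCAT could guide follow-up. If the raters can read part of the answer from later dates or later scores, good figures would not show that EMCAT alone carries the information.

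**Working it through.** The protocol states no expected accuracy, prevalence or sample size for this objective, so there is no figure to reproduce. The check compares the passages and then gives an illustration.

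**Step 1: dates against the outcome definition.** Raters see follow-up appointment dates (sections 9.12 and 11.4). The dates are collected at 24 weeks, so they can include visits arranged because of an earlier one. Of the five changes listed in section 7, one is the booking of further follow-up. A later date can therefore show that component directly. The other four (antibiotics, reoperation, investigation, hand therapy referral) cannot be read from a date in this direct way.

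**Step 2: scores after the visit.** EMCAT runs 12 × 7 = 84 days. For a visit at 2 weeks (day 14), 84 − 14 = 70 days, or 10 weeks, lie after the decision; that is 70/84 = 83% of the plot. Those scores may reflect the response to whatever was done. For a 12-week visit the same sum gives 84 − 84 = 0 days, so this route is essentially closed.

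**Step 3: what the date cue alone could achieve.** Suppose a rater ignores EMCAT and predicts a change only when a further date is shown. All three inputs are assumptions:
- p = share of patients with a change: 10–30%
- f = share of changed patients with a further date: 25–75%
- r = share of unchanged patients who also show a further (routine) date: 0–10%

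Formulas: sensitivity = f + (1 − f)r; specificity = 1 − r; accuracy = p × sensitivity + (1 − p) × specificity.

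- p = 0.20, f = 0.50, r = 0: sensitivity 0.50; specificity 1.00; accuracy 0.20 × 0.50 + 0.80 × 1.00 = 0.90. Always predicting no change would score 1 − p = 0.80.
- p = 0.20, f = 0.50, r = 0.10: sensitivity 0.50 + 0.50 × 0.10 = 0.55; specificity 0.90; accuracy 0.20 × 0.55 + 0.80 × 0.90 = 0.83.
- p = 0.10, f = 0.25, r = 0.10: sensitivity 0.25 + 0.75 × 0.10 = 0.325; specificity 0.90; accuracy 0.10 × 0.325 + 0.90 × 0.90 = 0.8425, below the 0.90 from always predicting no change.

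Over the whole grid, sensitivity runs from 25% to 77.5%, specificity from 90% to 100%, and accuracy from 72.8% to 97.5%, with no contribution from EMCAT.

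**Step 4: the cue added to real pre-visit information.** Let s0 be the sensitivity from pre-visit data alone. If the cue is independent of s0 and raters always act on it, apparent sensitivity = s0 + (1 − s0)f. With s0 = 0.4 and f = 0.25 this is 0.4 + 0.6 × 0.25 = 0.55. With s0 = 0.6 and f = 0.50 it is 0.6 + 0.4 × 0.50 = 0.80. These inputs are also assumed.

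**The case against.** The strongest reply is that the protocol never says raters see the entire trajectory or every date. Section 11.4 asks about a single follow-up appointment, section 7 mentions no dates, and a date is needed to locate the decision. This stands in part: full disclosure is an inference from the absence of a cut-off. But no section supplies a cut-off, and section 11.3 leaves no separate SAP to do so.

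A reader might go further than the documents allow in four ways:
- **That the material gives away the outcome as a whole.** Only one of the five listed changes can be read directly from a date, and the examples in section 12.5 do not name it. Where visits at 2 and 12 weeks are both routine, a second date alone is not decisive; extra or off-schedule dates are.
- **That a routinely booked second visit counts as a change.** Section 7 ties the change to the result of the follow-up appointment, which may exclude visits already planned. The text does not settle this, so it needs clarifying.
- **That visits after week 12 have no preceding EMCAT data.** Up to 12 weeks of daily scores precede them. What they lack is recent data.
- **That every measure must be inflated.** Routine dates in unchanged patients can lower specificity, and recovery after a treated problem could make a true change look benign. Kappa may rise because all raters share the cue, but this was not calculated.

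It is also fair that the objective is exploratory, with no hypothesis test or decision rule, and that the rating material is prepared only after the record review.

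**Conclusion.** The concern holds in this form: sections 9.12 and 11.4 give raters trajectories and appointment dates without a cut-off at the judged visit, while section 7 counts further follow-up as part of the outcome and describes the rater material differently. Later or off-schedule dates can directly disclose that one component. For early visits, up to about 10 weeks of later scores can indirectly disclose others. The accuracy measures would be biased, probably upward, and would not answer objective 5.

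The size cannot be derived from the documents; the figures above are illustrations on assumed inputs. The conclusion assumes that the plots and dates are shown as written, untruncated. It should be fixed, but it does not threaten the study: the objective is exploratory, and the primary and secondary analyses are untouched.

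**What to change.** Amend section 11.4, and sections 7 and 9.12 to match:
- For each judged appointment, show only EMCAT scores up to the day before it, mark that appointment's date, and hide all later dates.
- Make one prediction per appointment. Where a participant has several, have each rater complete the earlier one before seeing the later plot.
- State that follow-up already planned before the judged visit is not a change resulting from it.
- Make section 7 agree with sections 9.12 and 11.4 on whether raters see dates.
- Keep visits after week 12 but report them separately, since recent EMCAT data are lacking. A hard limit at day 84 is not needed and would drop 12-week visits held a few days late.

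The cost is slightly more plotting and rating work, with no new data collection. It should be done before any rater sees a plot, because a rater who has seen the later course cannot give an uninformed prediction afterwards.
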